#### Cost

To offset costs for those participating in the Mentoring Program, we have budgeted some funds for the group activities. We will also work to identify foundations that may be interested in donating funds to the program to further offset costs. We will also use a strategy similar to BBBS's of sending lists of free and inexpensive activity ideas directly to mentors each week for mentor's one-on-one meetings with their mentees.

#### Emotional or physical harm

The specific risks we will be monitoring are those described in the Child Welfare Information Gateway ([www.childwelfare.gov](http://www.childwelfare.gov)) publication "What is Child Abuse and Neglect? Recognizing the Signs and Symptoms." These include mentor behaviors such as blaming, belittling or berating the mentee, describing the mentee in very negative terms, and being secretive regarding the mentee. Potential mentee signs of harm include reluctance to be with the mentor, unexplained injuries, and reporting nightmares or bedwetting.

Multiple safeguards on multiple levels are in place to minimize risk to participants:

Mentor screening: Careful screening of mentors is one of the most important ways to mitigate risk. Friends for Youth's Mentoring Institute provides education on recommended best practices in the mentoring field. Their minimum and recommended screening standards can be found at [http://friendsforyouth.org/wp-content/uploads/2013/09/MentorScreening\\_RecommendedSteps.pdf](http://friendsforyouth.org/wp-content/uploads/2013/09/MentorScreening_RecommendedSteps.pdf). Our mentoring program's procedures match and even exceed their minimum and recommended standards.

Using a multifaceted approach to identify appropriate mentors, there are four phases mentor applicants must pass prior to acceptance:

- (1) A written application that includes open-ended questions about motivations for being a mentor and 3 measures: A quality of life measure (PedsQL) assessing the areas of physical health, and school/work, social and emotional functioning; a measure of self-efficacy for managing IBD; and the Volunteer Functions Inventory, which assesses motivations to volunteer.
- (2) An in-person interview that includes questions derived from national mentoring resources, including questions about motivations to be a mentor, information the applicant hopes to share with the mentee, how various challenges would be handled with a mentee (with specific examples), what qualities the applicant would like in a mentee, previous experience with children, and questions about the applicant's answers on the written application, including the measures.

Mentee screening: Eligibility criteria for mentees provide some protection from risk for both mentees and mentors. Eligibility criteria include no documented neurodevelopmental disorder or history of hospitalization for a psychiatric or behavioral disorder. Mentors are meant to be role models for living well with IBD, not peer psychotherapists. Children and adolescents who might need a higher level of support than the mentors can provide are not eligible for the study.

Many of the Friends for Youth Mentoring Institute screening recommendations occur after mentors have been screened and accepted into the program. We also have multifaceted safeguards in place for mentee safety after mentors have been screened and accepted into the program:

(1) Pre-match mentor training. The pre-match training session topics include relationship development and maintenance, communication, appropriate goals and expectations for the relationship, appropriate roles/boundary issues, self-management, and confidentiality, including limits of confidentiality such as abuse and self-harm. Procedures for managing these issues are detailed (briefly, the mentor is to call the program's "Urgent Response" phone line, and licensed program staff will manage the situation; more procedural detail is available). The training includes detailed descriptions of the program policies that applicants sign as a "commitment statement" when they become mentors. Mentors are given a program procedures manual as well as a folder for additional readings and the handouts they receive during the training session. These materials are also available on the program website.

(2) Post-match mentor training occurs approximately 6 months after the mentor and mentee introduction. This training addresses continued relationship development, communication, appropriate expectations and problem-solving. This information is also available online.

(3) Mentee and parent/caregiver training occurs prior to the structured mentor-mentee introduction and includes information about program expectations, expectations about the mentoring relationship, appropriate roles/boundary issues, tips for parents of mentees, and confidentiality, including limits of confidentiality such as abuse and self-harm. Mentees and parents are informed about the Urgent Response phone line (see below). Mentees also sign a "commitment statement."

(4) Urgent response phone line. A 24-hour "Urgent Response" line will be staffed by the Program Coordinator and Investigators for any participant (mentor, mentee, parent) to call at any time. Program Coordinators will typically have a background in social work and/or counseling and will be trained to manage situations that may arise via the Urgent Response line.

(5) Weekly reporting of mentee contact. Mentors will track the contact they have with their mentees every week via a secure online tracking system. The tracking system is a private section of the program website, making it easy for mentors to track their contact with their mentees. The tracking system consists of drop-down and text boxes in which the mentor describes the date and type of contact (e.g., in person, phone, text), overall rating of the contact, and what activity they participated in if it was an in-person contact. This information is automatically sent as an email to the Program Coordinator. No other mentors see this information. The contact will be monitored daily by the Program Coordinator and discussed with the Investigators in weekly meetings.

(6) Ongoing mentor check-ins. Mentors will receive supervision at least once per month via phone calls by the Program Coordinator which will be discussed with the Investigators in weekly meetings. There will be distinct processes for youth volunteers: Mentors  $\leq 18$  years will receive weekly phone supervision for the first month, then twice monthly supervision. Mentors  $> 18$  years will receive twice monthly phone supervision for the first 2 months, then monthly supervision. More frequent supervision will be provided if needed, for example, if a mentee is shy and the mentor would benefit from additional assistance in working with him or her, or if a family is disorganized and the mentor and mentee family would benefit from problem-solving aimed at developing strategies for scheduling weekly and in-person contact. The need for more frequent supervision will be determined by the Program Coordinator and PI, along with the mentor and/or mentee and family. The online tracking system will assist in identifying any issues. Supervision will be documented via structured supervision notes.

(7) Ongoing mentee check-ins. Mentees will be called once per month by the Program Coordinator, and these phone calls will be documented and discussed weekly with the Investigators. Mentees will be asked about activities they have participated in with their mentors as well as questions about their relationships with their mentors (e.g., "how are you and your mentor getting along?"). The final broad question is "do you have any (other) concerns?" in case the previous questions have not been sufficient to address any issues. Program Coordinators will have been trained via the Child Welfare Information Gateway publication "What is Child Abuse and Neglect? Recognizing the Signs and Symptoms" to recognize any responses that are concerning and suggest additional follow-up.

(8) Ongoing parent check-ins. Parents will be called once per month by the Program Coordinator,

and these phone calls will be documented and discussed weekly with the Investigators.

(9) Behavioral observation by the Investigators (licensed clinical psychologists) and Program Coordinators of mentor-mentee interactions will occur during the program's educational and recreational group events. Any observations of harm or potential harm (e.g., risky behavior at a recreational event) will be acted on immediately. Observations of interactions that are concerning (e.g., a mentee does not seem comfortable around a mentor) may be addressed at the event and/or addressed via check-in phone calls with the mentor, mentee, and parent, with calls made before regularly scheduled ones as needed.

(10) Specific program policies prohibiting harm are described during training and are listed in the program procedures manuals given to mentors, mentees and parents. Similarly, mentors and mentees are prohibited from being alone together, and must be in the company of others for their in-person get-togethers.

#### **4.0 Describe the clinical criteria for withdrawing an individual subject from the study due to safety or toxicity concerns:**

Mentors

Potential mentors can be withdrawn from the screening process at any time. As stated in the program procedures manual given to mentors, mentees and parents, mentors in the program must follow all program policies and procedures that are detailed in the mentor training and the manual. Any unacceptable behavior, as specified by but not limited to the Mentor Agreement, will result in a verbal or written warning and/or termination from participating mentoring program.

Mentees

Any mentees whose behavior becomes unsafe and interferes with appropriate participation in the program (i.e., behavior that now meets exclusion criteria) will be considered for withdrawal.

### **Clinical Research Summary**

- 1.0 \* Does this research involve a washout from medication taken prior to enrollment or assignment of subjects to a placebo or no-treatment arm?**  
 Yes  No
- 2.0 \* Will subjects in this research undergo any procedures involving radiation exposure?**  
 Yes  No
- 3.0 \* Will subjects in this research be exposed to radiation beyond that to which they would be exposed with standard care?**  
 Yes  No
- 4.0 \* Does this research involve the use of investigational drugs or biologics, that are not FDA-approved OR, if approved, not for this indication?**  
 Yes  No
- 5.0 \* Does this research involve the evaluation of an FDA-approved drug (regardless of whether it is to be used in accordance with its approved labeling)?**  
 Yes  No
- 6.0 \* Does this research involve the use of an investigational medical device, one that is not FDA-approved?**  
 Yes  No
- 7.0 \* Does this research involve the use of an FDA-approved medical device?**  
 No
- 8.0 \* Does this study involve a therapeutic intervention?**  
 Yes  No
- 9.0 \* Will a study sponsor cover all costs associated with drugs and/or devices used and all procedures performed under this protocol?**  
 Yes  No
- 10.0 \* Will any data and/or specimens be collected for genetic research?**  
 Yes  No

**11.0 \* Does this research involve healthy subjects?**

No

**Therapeutic Alternatives****1.0 \* What are possible therapeutic alternatives to participation in this study?**

Psychotherapy

**2.0 \* Are you aware of any competing protocols which target the same subject population locally?** Yes  No**If yes, please describe how you will prioritize subject entry among the various competing protocols:****Data and Safety Monitoring Plan****1.0 \* Check response below that will accurately reflect who monitors the data:**

Name

- 
- The study will be monitored only by the study investigators and/or sponsor.
- 
- The study will be monitored by at least one individual who is not associated with the study, but not by a formally constituted Data and Safety Monitoring Board (DSMB).
- 
- A formally constituted Data and Safety Monitoring Board (DSMB) will monitor the study.**

**2.0 If this research involves more than minimal risk to participants, provide a detailed description of provisions for monitoring data to ensure the safety of participants. Include: what are the qualifications of those who will monitor the data, what data will be monitored, how often will data be monitored and what endpoints will be monitored.**

The study statistician, [name] will monitor the study data. He has significant expertise in clinical trials and has collaborated on the design, power analysis and data analytic considerations for this proposal. Every 6 months, he will generate a random sample of 10% of the cases for whom data was collected in the previous 6 months at each site for audit. These cases will be audited for compliance with IRB requirements, conformance with informed consent requirements, verification of source documents, and investigator compliance. This is in addition to other routine checks in place such as double data entry and post-study-visit protocol and data checks. These checks will be conducted by PI's and research assistants.

**3.0 \* Summarize any pre-specified criteria for stopping or changing the study protocol due to safety concerns:**

Stopping or changing the study protocol will be discussed with the investigators and DSMB when/if any adverse events occur.

**4.0 \* Are there any plans to perform an interim efficacy analysis?** Yes  No**If you answered yes, please describe the plans to conduct an interim analysis:****Independent Monitor or DSMB****1.0 \* List the affiliations and qualifications of those monitors who are not associated with the study or describe the composition of the DSMB:**

The study will be monitored by a Data and Safety Monitoring Board (DSMB) comprised of the following members who have accepted positions on the DSMB:

[name], will serve as the Chair of the DSMB. [name] is an expert in the ethics of clinical research and the work of DSMBs. He has served as the Associate Dean for Clinical Research in the College of Medicine and the Director of Regulatory Knowledge and Ethics for the Center for Clinical and Translational Science at the Ohio State University. In these roles, he has provided guidance on a range of issues regarding the ethics of clinical research and the work of DSMBs. He has conducted many clinical trials in the area of HIV.

[name], MSPH, will serve as the Executive Secretary of the DSMB. [name] is a Professor of Pediatric Hematology and the Director of the Center for Clinical Effectiveness Research of the Children's Research Institute at the Medical College of Wisconsin/Children's Hospital of Wisconsin. She has experience with DSMBs, and with her own clinical trials as well as those those conducted in the Center for Clinical Effective Research, which she directs.

[name], ABPP, FAHS, will be the clinical trials expert on the DSMB. He is a Professor in the Department of Pediatrics of the University of Cincinnati, Cincinnati Children's Research Foundation Endowed Chair, and Scientific Director of Clinical Research and Trials at Cincinnati Children's. [name] has conducted multiple clinical trials, the results of which have been frequently cited and published in prestigious journals. He also trains future scientists in the conduct of clinical trials via the training grants he has received and the career development grants his early career mentees have received.

**2.0 \* Describe how frequently the independent monitor(s) or DSMB will meet and/or review study data:**

After an initial meeting shortly after the start of the study (within 3 months), the DSMB will meet every 6 months for the length of the study.

**3.0 \* Describe the type of data (e.g., blinded or unblinded) to which the independent monitor(s) or DSMB will have access:**

The DSMB will have access to unblinded data.

## Confidential Health Information

**1.0 \* Please mark all categories that reflect the nature of health information to be accessed and used as part of this research.**

Category

**Demographics (age, gender, educational level)**

**Diagnosis**

**Laboratory reports**

Radiology reports

Discharge Summaries

**Procedures/Treatments Received**

Category

- Dates related to course of treatment, (admission, surgery, discharge)**
- Billing Information
- Names of drugs and/or devices used as part of treatment**
- Location of treatment
- Name of treatment provider**
- Surgical Reports
- Other information related to course of treatment**
- None

**2.0 Please discuss why it is necessary to access and review the health information noted in your response above.**

Recruitment, and they are potential covariates, and outcomes of the study.

**3.0 \* Is the health information to be accessed and reviewed what is minimally necessary to achieve the goals of this research?**

Yes  No

**4.0 \* Will it be necessary to record information of a sensitive nature?**

Yes  No

**5.0 \* Do you plan to obtain a federally-issued Certificate of Confidentiality as an means of protecting the confidentiality of the information collected?**

Yes  No

## Protected Health Information Recording

**1.0 \* Please indicate which subject identifiers will be recorded for this research.**

Name

- Name**
- Complete Address**
- Telephone or Fax Number**
- Social Security Number
- Dates (treatment dates, birth date, date of death)**
- Email address , IP address or url**
- Medical Record Number or other account number**
- Health Plan Beneficiary Identification Number
- Full face photographic images and/or any comparable images (x-rays)
- Account Numbers
- Certificate/License Numbers
- Vehicle Identifiers and Serial Numbers (e.g. VINs, License Plate Numbers)
- Device Identifiers and Serial Numbers
- Biometric identifiers, including finger and voice prints
- Other number, characteristic or code that could be used to identify an individual
- None (Complete De-identification Certification Form)

**2.0**

**2.0 Check the appropriate category and attach the required form\* below. (choose one)**

Description

- Patient Authorization will be obtained. (Include the appropriate HIPAA language (see Section 14 of template) in the consent form OR attach the "HIPAA Authorization" form.)**

## Description

- Protocol meets the criteria for waiver of authorization. (Attach the "Waiver of Authorization Request" form.)
- Protocol is using de-identified information. (Attach the "De-Identification Certification" form.) (Checked "None" in 1.0 above)
- Protocol involves research on decedents. (Attach the "Research on Decedents Request" form.)
- Protocol is using a limited data set and data use agreement. (Complete the "Data Use Agreement" form, obtain other party's signature. Keep in study file."

**\*View Category Descriptions Here: [HIPAA Categories Description](#)**

### 2.1 Add the appropriate HIPAA forms:

Name Date Modified

There are no items to display

### 3.0 \* How long will identifying information on each participant be maintained?

Length of the study

### 4.0 \* Please describe any plans to code identifiable information collected about each participant.

Only research staff will have access to research data. The study coordinator will keep a password-protected database of all subjects who participate. Study data will be kept separately and filed with only a number for identification. The list of names associated with the identifying numbers will be kept separate and labeled with a code in such a way so that others cannot understand it. Access will be allowed for study personnel only.

### 5.0 \* Please check each box that describes steps that will be taken to safeguard the confidentiality of information collected for this research.

Name

- Research records will be stored in a locked cabinet in a secure location**
- Research records will be stored in a password-protected computer file**
- The list linking the assigned code number to the individual subject will be maintained separately from the other research data**
- Only certified research personnel will be given access to identifiable subject information**

### 6.0 \* Describe the provisions included in the protocol to protect the privacy interests of subjects, where "privacy interests" refer to the interest of individuals in being left alone, limiting access to them, and limiting access to their information. (This is not the same provision to maintain the confidentiality of data.)

There are risks related to loss of privacy and confidentiality, since participants will be interacting with other participants and potentially engaging in group activities. The privacy risk is well-described in the consent and assent forms. Participants will be informed that they will be interacting with other patients if they decide to participate in the program, thus other people will know that they have IBD and are participating in this project. If this is a concern, they can decline to participate with no adverse effects. Every effort will be taken to maintain confidentiality. In the mentoring program, confidentiality will be emphasized in training, supervision and group activities. Confidentiality reminders will occur at the beginning and end of group events. Confidentiality issues will also be an on-going topic during mentor supervision.

## Recruitment and Retention Tools

### 1.0 \* Describe local recruitment strategies/plans for potential study subjects and where recruitment will be done:

Youth participants: After diagnosis is confirmed, patients at two sites (NCH, CCHMC) participate in a "teaching visit" or educational group visit to learn about the disease and the clinic. On-going research at the clinic is also discussed, so we will approach patients about enrolling in the project at this time. Other potential youth participants will be approached via recruitment letter, brochure, phone call and/or clinic visit.

## Mentors:

-Potential mentors will be identified via the pediatric and adult gastroenterology clinics. Patients will be approached via recruitment letter, brochure, phone call and/or clinic visit, and we will hang flyers in clinics. We will also use hospital social media to advertise.

-We will distribute flyers and other materials (e.g., balloons, pins) at Crohn's and Colitis Foundation and other IBD-related events. We will advertise on Crohn's and Colitis Foundation and other IBD-related social media.

-We will advertise at local colleges via newsletters, service/volunteer fairs, bulletin boards, email lists, social media, student organizations such as the Psychology Club, and other media.

-Previous mentors and previous mentees who have turned 16 may be asked if they are interested in participating again as mentors.

-We will advertise the study to hospital employees (e.g., sending an "Everyone" email, advertising on internal hospital media).

-We will use ResearchMatch and VolunteerMatch.

-We will advertise on our lab websites and lab newsletters.

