## 4.0 If this research is hypothesis driven, succinctly state the hypothesis:

Hypothesis 1a: Participants in the Mentoring Program will have significantly improved QOL compared to those in the Educational Activity group post-intervention and 6 months later.

Hypothesis 1b: Participants in the Mentoring Program will have significantly improved functioning in typical life activities (i.e., functional abilities) and better disease outcomes (e.g., less severe disease as measured via biomarker and standardized indices) post-intervention and 6 months later.

Hypothesis 2a: Parents in the Mentoring Program will have significantly improved QOL compared to those in the Educational Activity group post-intervention and 6 months later.

Hypothesis 2b: The QOL of the mentors will significantly improve from baseline to post-intervention.

Hypothesis 3: Parent and child self-efficacy, illness uncertainty, coping, social support and child perceived stigma will mediate relationships between mentoring and outcomes. Sex will be explored as a moderator.

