## Finding Subjects

**1.0 \* Please check the box(es) below that best reflect how patients will be identified and recruited for participation.**

How subjects will be identified

- Potential subjects will self-refer in response to advertisements.**
- Subjects will roll-over from another research study.
- Potential subjects will be identified from a registry of individuals interested in research opportunities.**
- Medical records and/or other Institution sources (databases, billing records, pathology reports, admission logs, etc.) will be reviewed to identify potential participants. May involve access of records by individuals not involved in the patient's care.**
- Potential subjects will be identified by their treating physicians and referred to the researchers. Patients' private and identifiable information will not be shared prior to receiving permission from the patient to do so.**
- Potential subjects will be identified and approached during an inpatient or outpatient clinical visit by a member of the research team**
- Other**

**2.0 \* Do you assure the IRB that you acknowledge the need to address the potential for coercion and that you will employ reasonable and appropriate steps to emphasize the voluntary nature of participation?**

Yes  No

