**Inclusion and Exclusion Criteria****1.0 \* List the specific study inclusion criteria:**

Youth: Age 10 – 17 years with diagnosis of IBD

Mentors: Age 16-35 years, ≥1 year post-diagnosis, and pass screening process including a written application, background check, sex offender, social media, and child abuse registry check, interview, and character references

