**2.0 \* List the specific study exclusion criteria:**

- (1) Documented neurodevelopmental disorder, or
- (2) History of hospitalization for a psychiatric or behavioral disorders, or
- (3) Documented significant behavioral/emotional problems that would interfere with appropriate participation in the program, for example, behavioral/emotional problems that would interfere with group activities and/or would be beyond the scope of the training and supervision provided to mentors.

**3.0 \* Will participation in the research be limited to individuals who meet specific criteria related to age, gender, race, preferred language or any other demographic or socio-economic condition:**

Yes

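### Trial mentees aged 16 or over may be recruited as mentors before their own 6-month follow-up, and comparison youth are not barred, so the sustained-effect contrast can be contaminated

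*Combined protocol and SAP*

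**What the plan says.** Recruitment and Retention Tools, item 1.0, lists the sources of mentors. One is former participants: "Previous mentors and previous mentees who have turned 16 may be asked if they are interested in participating again as mentors". Another is general: "Potential mentors will be identified via the pediatric and adult gastroenterology clinics".

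The age ranges in Inclusion and Exclusion Criteria, item 1.0, overlap at 16 and 17. One line reads "Youth: Age 10 – 17 years with diagnosis of IBD" and the other "Mentors: Age 16-35 years, ≥1 year post-diagnosis, and pass screening process". The three exclusions in item 2.0 concern neurodevelopmental, psychiatric and behavioural problems. None concerns current, recent or pilot participation.

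Study Summary, item 3.0, puts both immediate and sustained effects in the primary aim. Hypothesis 1a in item 4.0 sets the quality-of-life (QOL) comparison at "post-intervention and 6 months later". Under Methods, item 1.0, the mentoring relationship lasts a year, with assessments at 12 months and 6 months after that. The analysis text in Methods, item 2.0, says nothing about youth who take up a mentor role during follow-up.

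**The concern.** A trial mentee becomes a previous mentee when the year ends, which is when the 6-month window opens. If that youth is 16 or over, the recruitment text allows an approach at once. As a mentor the youth would have training, supervision, group events and a new one-to-one relationship. The 6-month score would then mix durability of the first year with effects of further involvement.

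The comparison arm has a quieter opening. A comparison youth who is 16 or 17 falls within the mentor age range and attends the clinics where mentors are sought. Serving as a mentor would give that youth part of the program. The protocol otherwise keeps the arms apart, since the comparison group attends its educational events separately, but it does not carry that separation into mentor recruitment.

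The analysis cannot cleanly undo either exposure. Volunteering happens after randomisation and probably depends on how well the youth is doing, so removing those youths would itself create selection.

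**Working it through.** **Plan's own figure.** Sample Size Information, item 2.0, gives 94% power for d = 0.5 with 100 per arm, and 88% after 20% attrition (80 per arm), at a type I error of 0.05. With power ≈ Φ(d√(n/2) − 1.96):
- n = 100: 0.5 × √50 − 1.96 = 1.576, so 94.2% (94.0% by noncentral t).
- n = 80: 0.5 × √40 − 1.96 = 1.202, so 88.5% (88.2% by noncentral t).

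Both reproduce with a two-sided test. They apply to baseline to post-intervention only.

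**Timing.** The mentee route opens after month 12, so it cannot affect the month-12 outcome. The comparison route has no such limit: a comparison youth already 16 could in principle become a mentor before month 12.

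**Share old enough (assumption: ages uniform from 10 to just under 18 at baseline).** The share aged 16 or over after t years is (18 − (16 − t))/8.
- t = 0: 2/8 = 25%
- t = 1: 3/8 = 37.5%
- t = 1.5: 3.5/8 = 43.8%

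These are ceilings. Time since diagnosis, screening and willingness all reduce them.

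**Mentee route (assumptions: uptake 10-30% of those eligible at month 12; carry-on effect 0.3-0.5 SD).**
- Share of the mentoring arm: 0.375 × 0.10 = 3.8% to 0.375 × 0.30 = 11.3%, or about 4 to 11 of 100 youth.
- Shift in the 6-month contrast: 0.0375 × 0.3 = 0.011 SD to 0.1125 × 0.5 = 0.056 SD, upward.
- The standard error of a standardised difference is √(2/100) = 0.14 with 100 per arm and √(2/80) = 0.16 with 80, so even the top of the range is well under half a standard error.
- If the true sustained effect were zero and each such mentee gained 0.5 SD, the rejection rate with 80 per arm would be about 5.3% when 5% of the arm become mentors, and 6.1% when 10% do.

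**Comparison route (assumptions: a fraction c of the comparison arm receives the full mentoring effect; true effect 0.5 SD).** The contrast becomes 0.5(1 − c). With 80 per arm:

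| c | Effective d | Power |
|---|---|---|
| 0 | 0.500 | 88.5% |
| 5% | 0.475 | 85.2% |
| 10% | 0.450 | 81.2% |

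This shift is downward. It overstates the likely loss, because a mentor receives only part of what a mentee receives.

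**The case against.** **Pilot mentees may be all that was meant.** The form was written before enrolment, when the only previous mentees came from the pilot. That reading is plausible, but the sentence does not say so and it stays in force while trial mentees complete their year.

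**Screening is a real filter.** A reader might infer that nothing keeps trial youth out of the mentor pool. The documents do not support that. Mentors must be at least 16, a year past diagnosis and managing their disease well, and must pass an application, interview, checks and observed training. In the pilot, 8 of 26 written applicants (31%) withdrew or were rejected. Staff would very likely recognise a trial youth who applied. All this limits numbers, but no stated rule says such a youth would be refused or deferred.

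**The comparison route is inferred.** It rests on overlapping ages and general clinic recruitment. The sentence on former participants does not name comparison youth. This is fair, and that route is the weaker one.

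**Volunteering may be part of the effect.** Becoming a mentor can be seen as a consequence of assignment, which an as-randomised comparison properly includes. That is coherent, but the 6-month result would then be the effect of assignment including later mentor service. The plan describes it as sustained effect and records no such service.

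**A rule may exist elsewhere.** The handbook, procedures manuals, consent forms and mentor information sheet were not available, so this cannot be excluded.

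**Pilot mentees enrolling as trial youth.** A reader might infer that these also distort the 6-month result in particular. The roll-over box under Finding Subjects, "Subjects will roll-over from another research study", appears unselected. That does not exclude anyone, but pilot participants are not a stated source of youth. Their exposure would precede randomisation and so be balanced in expectation. It could only dilute, and would do so at both time points.

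**Conclusion.** The concern holds in a limited form. The text permits a trial mentee aged 16 or over to become a mentor before the 6-month assessment, and it does not bar an eligible comparison youth. Neither the criteria nor the analysis plan deals with this.

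The effect is probably small: about 0.01-0.06 SD for the mentee route. That range rests on assumed uniform ages, 10-30% uptake and a 0.3-0.5 SD carry-on effect, none of which the documents supply. The upper carry-on value is close to the pilot's whole-program QOL effect of 0.52, so the top of the range is generous, the more so because a new mentor must be screened, trained and matched within 6 months.

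It would be tempting to call this a bias in favour of mentoring. The documents do not support that, because the mentee route inflates, the comparison route dilutes, and the net direction is unknown. Nor is the powered test at risk from the mentee route. Only the less likely comparison route could reach it. This is a low-severity point, worth acting on because prevention is cheap and later repair is not.

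**What to change.** Add one sentence to Inclusion and Exclusion Criteria, item 1.0 (mentor criteria), and to the mentor section of Recruitment and Retention Tools, item 1.0: no youth randomised in this trial, in either arm, may be recruited or serve as a mentor until his or her own 6-month assessment is complete. If the sentence on previous mentees was meant for pilot mentees only, say so there.

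Record any mentor service by a randomised youth that begins before that assessment, with its start date, and report the count by arm.

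The cost is a slightly smaller or delayed mentor pool; the youths concerned can still become mentors afterwards.

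Excluding pilot mentees from youth enrolment is optional. It would remove a possible dilution of both contrasts at the price of a few potential participants.
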